6.2 DATA SHARING PLANS

6.2.1 Human Data Sharing Plan

What data will be shared?

I will share human data generated in this research for future research as follows:

Coded, linked data in an NIH-funded or approved public repository.

Coded, linked data in another public repository

Coded, linked data in BTRIS (automatic for activities in the Clinical Center)

Identified or coded, linked data with approved outside collaborators under appropriate agreements.

How and where will the data be shared?

Data will be shared through:

An NIH-funded or approved public repository. Insert name or names: [ClinicalTrials.gov](#), [dbGaP](#).

BTRIS (automatic for activities in the Clinical Center)

Approved outside collaborators under appropriate individual agreements.

Publication and/or public presentations.

When will the data be shared?

Before publication.

At the time of publication or shortly thereafter.

6.2.2 Genomic Data Sharing Plan

The NIH Genomic Data Sharing plan does not apply to this protocol.

6.3 RESPONSE CRITERIA

6.3.1 Response Assessments

Tumor response will be assessed radiographically after cycle 2 and 4 treatments are completed by the investigator using the Immune-Modified Response Evaluation Criteria In Solid Tumors, i.e., imRECIST criteria [\[88\]](#) for Immune-related Best Overall Response (irBOR, Section **6.4.1**) will be derived based on reported lesion responses at different evaluation time points from the first trial treatment administration until immune-related disease progression per imRECIST [\[88\]](#) according to the following rules:

- irCR = at least two radiographic determinations of CR at least 4 weeks apart and before irPD
- irPR = at least two radiographic determinations of PR or better at least 4 weeks apart and before irPD (and not qualifying for an irCR)
- irSD = at least one radiographic assessment of SD (or better) ≥ 6 weeks after the first trial treatment administration and before irPD (and not qualifying for irCR or irPR).
- irPD = at least two consecutive radiographic determinations of PD at least 4 weeks apart.

Only tumor assessments performed before the start of any further anti-cancer treatment will be considered in the assessment of irBOR.

Immune-related Objective Response (irOR) is defined as irCR or irPR according to irRECIST from the first trial treatment administration until irPD or death due to any cause. Both irCR and irPR must be confirmed by repeat assessments performed no less than 4 weeks after the criteria for immune-related response are first met. Also, irPD must be confirmed by a second, consecutive assessment at least 4 weeks apart. Immune-related OR rate (irORR) is the proportion of subjects with irOR in the analysis set.

6.3.2 Treatment Beyond Radiographic Progression

Recognition of unconventional response events mainly overall tumor regression after the appearance of new lesions that previously were assessed as progressive disease by RECIST criteria led to the development of Immune-related RECIST (irRECIST) [89] and the Immune-modified RECIST (imRECIST) criteria [88]. Adoption of these disease criteria have been seen to allow a better assessment of the clinical efficacy of immunotherapy by capturing additional data from patients who experienced a tumor flare or delayed impact of the evolving immune response mostly in terms of improved DCR and PFS. In order for this approach to not negatively affect patient safety certain criteria must be fulfilled to safely allow treatment beyond conventionally assessed disease progression. Patients who are treated beyond RECIST defined progressive disease must be stable performance status without evidence of clinical deterioration or have any new physiology process that requires urgent additional therapy. Patients will have a follow-up restaging assessment after the completion of their next cycle of treatment (≥ 4 weeks) to confirm their disease has not progressed further and they can safely continue treatment.

Patient will be re-evaluated for response as outlined in the Study Calendar, **APPENDIX F**.

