3 STUDY IMPLEMENTATION

3.1 STUDY DESIGN

In this Phase II trial of combination rhIL-15 and avelumab in patients with relapsed or refractory metastatic PD-L1+ ccRCC, IL-15 will be administered by CIV. The trial will begin with a small safety run-in cohort with a rhIL-15 starting dose of 2 mcg/kg/day, and a second dose level of 4 mcg/kg/day (the desired Phase II dose). There is clinical experience for the combination of anti-PD1 plus IL-15, but there is no prior safety experience for the combination of avelumab and E. coli derived rhIL-15. Consequently, the first 3 patients will begin CIV rhIL-15 treatment at a dose of 2 mcg/kg/day on days 1-5 and avelumab (800mg, by IV) on day 8 and 22 of the 28-day cycle (i.e., every 2 weeks). If one of these patients has a dose limiting toxicity (DLTs), three additional patients will be treated to establish the safety of the combination. Assuming there are no DLTs, subsequent patients will be treated at the 4 mcg/kg/day dose level. Again, the safety of this dose of rhIL-15 in combination will be established in a 3 to 6 patient cohort to confirm this treatment regimen does not pose unacceptable risk to the enrolled subjects. If a second patient in these safety run-in cohorts at either the 2 or 4 mcg/kg dose level experiences a DLT all treatment and enrollment will be halted to review the data and determine if further clinical evaluation of the combination should be attempted. Treatment will continue for a maximum of 4 cycles or until toxicity (i.e., dose limiting toxicity as found in Section 3.1.1 or toxicity requiring hold as defined in Section 3.3) or progressive disease.

After the safety of the 4 mcg/kg dose level is established all subsequent patients will be treated with CIVrhIL-15 at the dose of 4 mcg/kg on days 1-5 (120 hours) and avelumab (800mg, by IV) on day 8 and 22 of each 28-day cycle for a maximum of 4 cycles (in the absence of toxicity requiring hold as defined in Section 3.3 or progressive disease).

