3.5 ON STUDY EVALUATIONS

Prior to avelumab administration (Day 8 and 22), pre-dose assessments must be performed (up to 3 days prior). After Cycle 1, pre-dose assessments may be performed up to 3 days prior to a cycle except where otherwise noted. In the event that the patient's condition is deteriorating, laboratory evaluations should be repeated within 48 hours prior to initiation of the next cycle of therapy. The results from all procedures/tests must be reviewed prior to initiation of each cycle of treatment for consideration of dose modifications and delay of therapy.

Treatment with rhIL-15 and avelumab will continue for 4 cycles or until disease progression, unacceptable treatment-related toxicity or other reasons outlined in Section [3.9.1](#).

Refer to the Study Calendars (Section [APPENDIX F](#)) for a complete list of procedures to be performed at each scheduled study visit. See also Section [5](#) for all samples to be collected for correlative research. During treatment, it is expected that all laboratory and clinical assessments be conducted at the NIH (including post-treatment imaging evaluations); results from outside NIH will only be accepted at the discretion of the investigator.

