3.6 POST-TREATMENT EVALUATIONS

Post treatment evaluations (i.e., End of Treatment Visit) will be performed approximately 30 days after the last dose of protocol treatment. If a subject initiates a new anti-cancer therapy within 30 days after the last dose of trial treatment, the 30-day safety follow-up visit must occur before the first dose of the new therapy, if possible. If the patient cannot return to the Clinical Center for this visit, a request will be made to have a local physician or laboratory collect a CBC with differential and send the results. If this is not possible, patients may be assessed by telephone or email for symptoms.

Unless otherwise noted, follow-up will occur at the following time point: every 60 days (\pm 7 days) for 6 months; then every 90 days (\pm 14 days) for 2 years; then every six months (\pm 28 days) for the duration of the study until the start of a new anti-neoplastic therapy, disease progression, death or end of study. Any other evaluations and tests should be performed as clinically indicated.

Upon disease progression or initiation of other anti-cancer therapy, contact will be for survival only until the subject is off study (i.e., every 3 months [\pm 4 weeks]) for the duration of the study. See Study Calendar (Section [APPENDIX F](#)) for additional information. Any adverse events

which are present at the time of discontinuation should be followed in accordance with the safety requirements.

Patients who are removed from study before completing protocol treatment will be followed until completion of the Safety Follow-up Visit or until death, whichever occurs first. Patients removed from study for unacceptable adverse event(s) will be followed until resolution or stabilization of the adverse event.

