3.9.1 Criteria for removal from protocol therapy

In the absence of treatment delays due to adverse event(s), treatment may continue for 4 cycles or until one of the following criteria applies. Patients who meet the following criteria should be discontinued from protocol therapy:

- Completion of protocol therapy (i.e., up to 4 cycles)
- Clinical or Disease progression
- Intercurrent illness that prevents further administration of treatment
- Unacceptable toxicities as listed in Section **3.1.1** or those toxicities listed in Section **3.3** that require treatment to be stopped.
- Subject's request to withdraw from protocol therapy
- Investigator's decision to withdraw the patient
- Subject's non-compliance with trial treatment or procedure requirements that requires removal in the opinion of the PI
- Pregnancy
- Study is cancelled for any reason
- The drug manufacturer can no longer prove the study agent

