10 STATISTICAL CONSIDERATIONS

10.1 STATISTICAL HYPOTHESES

10.1.1 Primary Endpoints

Overall Response (CR + PR) by irRECIST 1.1 criteria in patients who receive at least 1 cycle of therapy with the 4 mcg/kg dose of rhIL-15.

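### The sections disagree on which progression event ends therapy and tumour follow-up, so whether a response after first RECIST progression can be observed and confirmed depends on the section followed

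*Combined protocol and SAP*

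**What the plan says.** **Stopping therapy.** Section 3.1: "Treatment will continue for a maximum of 4 cycles or until toxicity" or progressive disease. Section 3.5: "Treatment with rhIL-15 and avelumab will continue for 4 cycles or until disease progression", among other reasons. Section 3.9.1: "Patients who meet the following criteria should be discontinued from protocol therapy", and the list includes "Clinical or Disease progression". None of the three says whether RECIST progression or confirmed irPD is meant, and none refers to 6.3.2.

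**Continuing therapy.** Section 6.3.2 sets conditions for going on: "Patients who are treated beyond RECIST defined progressive disease must be stable performance status without evidence of clinical deterioration". It requires restaging after the next cycle, at least 4 weeks later.

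**Defining progression and response.** Section 6.3.1: "irPD must be confirmed by a second, consecutive assessment at least 4 weeks apart". The same section requires two determinations at least 4 weeks apart, before irPD, for irCR or irPR.

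**Follow-up.** Section 3.6: "Upon disease progression or initiation of other anti-cancer therapy, contact will be for survival only until the subject is off study". Section 3.6.4 makes the same move only once progression is confirmed. The calendar (Appendix F) places disease evaluations after cycles 2 and 4. Its footnote 5 asks for a confirmatory scan 4 weeks after a first objective response and does not mention confirming progression.

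**Primary endpoint.** Section 10.1.1: "Overall Response (CR + PR) by irRECIST 1.1 criteria in patients who receive at least 1 cycle of therapy with the 4 mcg/kg dose" of rhIL-15.

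**The concern.** A clinically stable patient with RECIST progression on the scan after cycle 2 should stop under 3.9.1 and may continue under 6.3.2. Under 3.6 that patient passes to survival contact at once. Under 3.6.4 this waits for confirmation, and 6.3.1 cannot call the event irPD without a second scan.

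This reaches the primary endpoint because irRECIST was chosen to credit responses that follow apparent progression. Under 10.3.2, patients who discontinue and are not restaged count as non-responders, so an unobserved response is scored as a failure. The trial is open-label and single-arm, the investigator assesses response, and the decision thresholds are 1 of 9 and 3 of 17. Two investigators following different sections could record different outcomes for the same patient.

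**Working it through.** **1. The sections side by side**, for a stable patient with first RECIST progression after cycle 2:

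| Question | One set of sections | The other set |
|---|---|---|
| Does therapy stop? | Yes: 3.1, 3.5, 3.9.1 | Not necessarily: 6.3.2 |
| When does survival-only contact begin? | At progression: 3.6 | At confirmed progression: 3.6.4 |
| Is a further scan required? | Not under 3.6 | Yes: 6.3.1 (irPD), 6.3.2 (restaging) |

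**2. Timeline on nominal days.** Cycles last 28 days, so the scan after cycle 2 falls at about day 56. The last avelumab dose by then is cycle 2 day 22, which is day 28 + 22 = 50.
- *Following 3.9.1 and 3.6.* The end-of-treatment visit is 30 days after the last dose, at about day 80, or 24 days after the first progression scan. The calendar appears to mark imaging at this visit (the table is broken in the extracted text). That scan alone cannot give the two determinations needed for irPR or irCR. If it showed a response, footnote 5 would call for another scan 4 weeks later, at about day 108, but 3.6 has by then limited contact to survival.
- *Following 6.3.2.* Restaging after cycle 3 (about day 84) and the scan after cycle 4 (about day 112) are 28 days apart and can supply both determinations.
- *Progression first seen after cycle 4.* Therapy is already complete, so only the imaging conflict between 3.6 and 3.6.4 remains.

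**3. The plan's own design.** Inputs from 10.2: null rate 5%, target 25%, stop at 0 of 9, success at 3 or more of 17.

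P(success) = P(Bin(17, p) ≥ 3) − P(Bin(9, p) = 0) × P(Bin(8, p) ≥ 3)
- Early stop at p = 0.05: 0.95^9 = 0.630 (stated 63%).
- Passing stage 1 at p = 0.25: 1 − 0.75^9 = 0.925 (stated 92%).
- Type I error: 0.0503 − 0.6302 × 0.0058 = 0.0466 (limit 5%).
- Power: 0.836 − 0.075 × 0.321 = 0.812 (stated 80%).

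The design reproduces, and the sample size is not in question.

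**4. Upper bound on the loss.** Let f be the share of true responders who first show RECIST progression, and suppose all of them are lost. The observable rate is 0.25 × (1 − f), and the expected loss among 17 patients is 17 × 0.25 × f.

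| f (assumed) | Observable rate | Expected responders lost | Passing stage 1 | Power |
|---|---|---|---|---|
| 0 | 0.250 | 0 | 0.925 | 0.812 |
| 5% | 0.2375 | 0.21 | 0.913 | 0.781 |
| 10% | 0.225 | 0.43 | 0.899 | 0.745 |
| 20% | 0.200 | 0.85 | 0.866 | 0.663 |

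Losing responses can only lower the count, so under the null the chance of success stays at or below 0.0466.

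**The case against.** The best defence is that 6.3.2 is a specific exception qualifying the general stopping lists. On that reading, progression throughout means confirmed irPD; 3.6.4 uses the word confirmed, and the conditions in 6.3.2 fit the removal criterion for clinical progression. This is coherent and may be what was intended. But 3.1, 3.5, 3.6 and 3.9.1 do not say it, and the best-response table in 6.3.7 still scores any new lesion as progression.

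A reader might infer that these patients are never rescanned and their responses never counted. The documents do not support that. The calendar appears to keep imaging at the end-of-treatment visit, footnote 5 provides for a confirmatory scan, and 6.3.1 closes best response at irPD or further anti-cancer treatment, not at first RECIST progression. Loss is possible, not certain.

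A reader might also take 0.75 or 0.66 as the trial's real power. Those figures rest on an undocumented share and on 6.3.2 never being used. Section 6.3.2 itself says the immune-adapted criteria add information mainly on disease control and progression-free survival, which suggests a modest effect on response rate. It is also true that a single patient can move 3 of 17 to 2 of 17 under any misclassification, so that does not measure this defect.

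**Conclusion.** The conflict stands as an inconsistency in the current text that bears on the primary endpoint. It affects only patients whose first event is RECIST progression and who might respond later; other responses are observed under either reading. The direction is conservative: a lower observed response rate and lower power, with no inflation of type I error. The size is unknown. The upper bound is a fall in power from 0.81 to 0.78, 0.75 or 0.66 for shares of 5%, 10% or 20%, assuming both the share and complete loss. The inconsistency does not depend on those figures. It merits correction because a wording change would remove the dependence of the result on which section is followed.

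**What to change.** Reconcile 3.1, 3.5, 3.6, 3.6.4, 3.9.1 and 6.3.2 so that they name the same progression event and refer to one another. Which event ends therapy is for the clinical team to decide. Separately, state in 3.6 and in the study calendar that tumour imaging continues until irPD is confirmed, as 6.3.1 already requires, or until new anti-cancer therapy starts, whatever the treatment status. All patients are then assessed for the primary endpoint on the same footing.

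The cost is mainly wording. It may add an occasional off-treatment scan, which should be checked against the up to seven additional CT scans and about 9.1 rem disclosed in 12.3.3.

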6.3.3 Disease Parameters for RECIST criteria

Measurable disease: Measurable lesions are defined as those that can be accurately measured in at least one dimension (longest diameter to be recorded) as ≥ 20 mm by chest x-ray, as ≥ 10 mm with CT scan, or ≥ 10 mm with calipers by clinical exam. All tumor measurements must be recorded in millimeters (or decimal fractions of centimeters).

Malignant lymph nodes: To be considered pathologically enlarged and measurable, a lymph node must be ≥ 15 mm in short axis when assessed by CT scan (CT scan slice thickness recommended to be no greater than 5 mm). At baseline and in follow-up, only the short axis will be measured and followed.

Non-measurable disease: All other lesions (or sites of disease), including small lesions (longest diameter <10 mm or pathological lymph nodes with ≥ 10 to <15 mm short axis), are considered non-measurable disease. Bone lesions, leptomeningeal disease, ascites, pleural/pericardial effusions, inflammatory breast disease, and abdominal masses (not followed by CT or MRI), are considered as non-measurable.

Note: Cystic lesions that meet the criteria for radiographically defined simple cysts should not be considered as malignant lesions (neither measurable nor non-measurable) since they are, by definition, simple cysts.

‘Cystic lesions’ thought to represent cystic metastases can be considered as measurable lesions, if they meet the definition of measurability described above. However, if non-cystic lesions are present in the same patient, these are preferred for selection as target lesions.

Target lesions: All measurable lesions up to a maximum of 2 lesions per organ and 5 lesions in total, representative of all involved organs, should be identified as **target lesions** and recorded and measured at baseline. Target lesions should be selected on the basis of their size (lesions with the longest diameter), be representative of all involved organs, but in addition should be those that lend themselves to reproducible repeated measurements. It may be the case that, on occasion, the largest lesion does not lend itself to reproducible measurement in which circumstance the next largest lesion which can be measured reproducibly should be selected. A sum of the diameters (longest for non-nodal lesions, short axis for nodal lesions) for all target lesions will be calculated and reported as the baseline sum diameters. If lymph nodes are to be included in the sum, then only the short axis is added into the sum. The baseline sum diameters will be used as reference to further characterize any objective tumor regression in the measurable dimension of the disease.

Non-target lesions: All other lesions (or sites of disease) including any measurable lesions over and above the 5 target lesions should be identified as **non-target lesions** and should also be recorded at baseline. Measurements of these lesions are not required, but the presence, absence, or in rare cases unequivocal progression of each should be noted throughout follow-up.

6.3.4 Methods for Evaluation of Measurable Disease

All measurements should be taken and recorded in metric notation using a ruler or calipers. All baseline evaluations should be performed as closely as possible to the beginning of treatment and never more than 4 weeks before the beginning of the treatment.

The same method of assessment and the same technique should be used to characterize each identified and reported lesion at baseline and during follow-up. Imaging-based evaluation is preferred to evaluation by clinical examination unless the lesion(s) being followed cannot be imaged but are assessable by clinical exam.

Clinical lesions: Clinical lesions will only be considered measurable when they are superficial (e.g., skin nodules and palpable lymph nodes) and 10 mm diameter as assessed using calipers (e.g., skin nodules). In the case of skin lesions, documentation by color photography, including a ruler to estimate the size of the lesion, is recommended.

Chest x-ray: Lesions on chest x-ray are acceptable as measurable lesions when they are clearly defined and surrounded by aerated lung. However, CT is preferable.

Conventional CT and MRI: This guideline has defined measurability of lesions on CT scan based on the assumption that CT slice thickness is 5 mm or less. If CT scans have slice thickness greater than 5 mm, the minimum size for a measurable lesion should be twice the slice thickness. MRI is also acceptable in certain situations (e.g. for body scans).

Use of MRI remains a complex issue. MRI has excellent contrast, spatial, and temporal resolution; however, there are many image acquisition variables involved in MRI, which greatly impact image quality, lesion conspicuity, and measurement. Furthermore, the availability of MRI is variable globally. As with CT, if an MRI is performed, the technical specifications of the scanning sequences used should be optimized for the evaluation of the type and site of disease. Furthermore, as with CT, the modality used at follow-up should be the same as was used at baseline and the lesions should be measured/assessed on the same pulse sequence. It is beyond the scope of the RECIST guidelines to prescribe specific MRI pulse sequence parameters for all scanners, body parts, and diseases. Ideally, the same type of scanner should be used, and the image acquisition

protocol should be followed as closely as possible to prior scans. Body scans should be performed with breath-hold scanning techniques, if possible.

PET-CT: At present, the low dose or attenuation correction CT portion of a combined PET-CT is not always of optimal diagnostic CT quality for use with RECIST measurements. However, if the site can document that the CT performed as part of a PET-CT is of identical diagnostic quality to a diagnostic CT (with IV and oral contrast), then the CT portion of the PET-CT can be used for RECIST measurements and can be used interchangeably with conventional CT in accurately measuring cancer lesions over time. Note, however, that the PET portion of the CT introduces additional data which may bias an investigator if it is not routinely or serially performed.

Ultrasound: Ultrasound is not useful in assessment of lesion size and should not be used as a method of measurement. Ultrasound examinations cannot be reproduced in their entirety for independent review at a later date and because they are operator dependent, it cannot be guaranteed that the same technique and measurements will be taken from one assessment to the next. If new lesions are identified by ultrasound in the course of the study, confirmation by CT or MRI is advised. If there is concern about radiation exposure at CT, MRI may be used instead of CT in selected instances.

FDG-PET: While FDG-PET response assessments need additional study, it is sometimes reasonable to incorporate the use of FDG-PET scanning to complement CT scanning in assessment of progression (particularly possible 'new' disease). New lesions on the basis of FDG-PET imaging can be identified according to the following algorithm:

- a. Negative FDG-PET at baseline, with a positive FDG-PET at follow-up is a sign of PD based on a new lesion.
- b. No FDG-PET at baseline and a positive FDG-PET at follow-up: If the positive FDG-PET at follow-up corresponds to a new site of disease confirmed by CT, this is PD. If the positive FDG-PET at follow-up is not confirmed as a new site of disease on CT, additional follow-up CT scans are needed to determine if there is truly progression occurring at that site (if so, the date of PD will be the date of the initial abnormal FDG-PET scan). If the positive FDG-PET at follow-up corresponds to a pre-existing site of disease on CT that is not progressing on the basis of the anatomic images, this is not PD.
- c. FDG-PET may be used to upgrade a response to a CR in a manner similar to a biopsy in cases where a residual radiographic abnormality is thought to represent fibrosis or scarring. The use of FDG-PET in this circumstance should be prospectively described in the protocol and supported by disease-specific medical literature for the indication. However, it must be acknowledged that both approaches may lead to false positive CR due to limitations of FDG-PET and biopsy resolution/sensitivity.

Note: A 'positive' FDG-PET scan lesion means one which is FDG avid with an uptake greater than twice that of the surrounding tissue on the attenuation corrected image.

